#### Treatment-Related AE

A treatment-related AE is any treatment-emergent adverse event that per investigator review has a reasonable possibility of being caused by the investigational product.

#### Dose Limiting Toxicities (DLT)

**DLT will be determined by “Is this event a Dose Limiting Toxicity (DLT)?” equal to “Yes” on the Events eCRF. Investigators will determine whether an adverse event qualifies as a DLT per protocol Section 6.2.1.3**

### Maximum Tolerated Dose (MTD)

The MTD is defined as the highest dose level whose DLT rate has the highest probability of the target TPI, an excessive/unacceptable TPI of  $< 0.25$ , and a minimum of 6 subjects have been treated at the MTD.

### Overall Response

Overall response is defined as achieving any of the following response: CR, CRh\*, CRi or MLFS.

### Duration of Response (DOR)

Duration of response is defined as the interval from the date of the first disease assessment indicating an overall response to the first documented relapse or death due to any cause, whichever occurs first. Subjects without relapse or death until the analysis data cut-off date will be censored at the last adequate disease assessment date. Only subjects with a response will be evaluated for DOR.

DOR time in days = earlier of (date of first relapse or disease progression or death or date of censoring) – date of the first observation of overall response + 1.

### Time to Response (TTR)

Time to response defined as the interval from the first administration of AMG 673 to the first documentation of response. Time to response is evaluated only for subjects who achieved a response.

Time to response is calculated as the number of days:  
(date of first response – date of study day 1 + 1).

### Time to Progression (Event-free Survival):

Event-free survival (EFS) is defined as the interval from first administration of AMG 673 to the earliest of date of treatment failure, relapse for responders, or death due to any cause. Censoring is at the last evaluable post-baseline response assessment; otherwise, at first administration of AMG673. For non-responders, the event date for treatment failure is assigned as the date of first administration of AMG 673.

Event-free Survival in days = earlier of (date of treatment failure or relapse or death or date of censoring) – date of the first administration of AMG 673 + 1.

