10.1.2 Analysis Sets

The analysis of all endpoints, unless noted otherwise, will be conducted on the Safety Analysis Set defined as all subjects that are enrolled and receive at least 1 dose of AMG 673.

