Appendix E. Revised International Working Group Response Criteria Revised Response Criteria

Category	Definition
Complete remission (CR) ¹	Bone marrow blasts < 5%; absence of blasts with Auer rods; absence of extramedullary disease; absolute neutrophil count > 1.0 x 10 ⁹ /L; platelet count > 100 x 10 ⁹ /L; independence of red cell transfusions
CR with incomplete recovery (CRi) ²	All CR criteria except for residual neutropenia (< 1.0 x 10 ⁹ /L) or thrombocytopenia (< 100 x 10 ⁹ /L)
Morphologic leukemia-free state ³	Bone marrow blasts < 5%; absence of blasts with Auer rods; absence of extramedullary disease; no hematologic recovery required
Partial remission	Relevant in the setting of phase I and II clinical trials only; all hematologic criteria of CR; decrease of bone marrow blast percentage to 5% to 25%; and decrease of pretreatment bone marrow blast percentage by at least 50%
Cytogenetic CR ⁴	Reversion to a normal karyotype at the time of morphologic CR (or CRi) in cases with an abnormal karyotype at the time of diagnosis; based on the evaluation of 20 metaphase cells from bone marrow
Molecular CR ⁵	No standard definition; depends on molecular target

Approved

Treatment Failure Criteria

Category	Definition
Resistant disease (RD)	Failure to achieve CR or CRi (general practice; phase II/III trials), or failure to achieve CR, CRi, or PR (phase I trials); only includes patients surviving > 7 days following completion of initial treatment, with evidence of persistent leukemia by blood and/or bone marrow examination
Death in aplasia	Deaths occurring > 7 days following completion of initial treatment while cytopenic; with an aplastic or hypoplastic bone marrow obtained within 7 days of death, without evidence of persistent leukemia
Death from indeterminate cause	Deaths occurring before completion of therapy, or <7 days following its completion; or deaths occurring > 7 days following completion of initial therapy with no blasts in the blood, but no bone marrow examination available Patients who do not complete the first course of therapy
Relapse ⁶	Bone marrow blasts > 5%; or reappearance of blasts in the blood; or development of extramedullary disease
Molecular or cytogenetic relapse	Reappearance of molecular or cytogenetic abnormality

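### The SAP's event-free survival definition gives two conflicting scores, censored or failed on day 1, to a living treated subject who leaves with no evaluable response assessment

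*SAP*

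**What the plan says.** SAP section 5, under Time to Progression (Event-free Survival), starts the clock at the first dose and stops it at the "earliest of date of treatment failure, relapse for responders, or death due to any cause". Two adjacent sentences then deal with subjects who have no dated relapse or death:

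- Censoring: "Censoring is at the last evaluable post-baseline response assessment; otherwise, at first administration of AMG673".
- Failure: "For non-responders, the event date for treatment failure is assigned as the date of first administration of AMG 673".

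The time in days is the "earlier of (date of treatment failure or relapse or death or date of censoring"), minus the first-dose date, plus 1.

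The EFS definition does not define non-responder or treatment failure and does not point to Protocol Appendix E for either. SAP section 10 explains the change from time to progression: EFS is meant to deal with relapsed or refractory subjects who are already progressing at entry and never respond.

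Protocol 10.1.2 puts all endpoints, unless noted otherwise, on the Safety Analysis Set, "defined as all subjects that are enrolled and receive at least 1 dose of AMG 673". SAP 9.5.2 tabulates the response proportion for subjects treated at the MTD/RP2D. It plans per-subject listings of the time endpoints for everyone, allows a Kaplan-Meier curve with 80% intervals, and calls the efficacy analyses exploratory.

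**The concern.** The second half of the censoring sentence applies only when there is no evaluable post-baseline assessment. A subject who has died has an event. An assessed non-responder is settled by the formula, because the day-1 failure date precedes the last assessment date. Two kinds of subject remain: those who left the study alive and unassessed, and those still on study awaiting a first assessment at the data cut-off. At the primary analysis every subject has had the opportunity for up to 2 cycles or has terminated (SAP 7.2), so the second kind should be rare, and the clause would then mainly govern subjects who left.

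A subject who left alive and unassessed has no observed response, and is the kind of subject EFS was adopted to count. Censoring that subject on day 1, while assessed non-responders fail on day 1, lifts the curve at every later week. Even if no curve is drawn, the listing needs an event or censoring status for each subject.

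**Working it through.** **1. Can the case arise?** In the two-dose Schedule A cycle the first on-treatment disease assessment is on day 14 (Protocol 6.2.1.1.1). In Schedule B the cycle 1 marrow follows the last cycle 1 dose, planned for day 14 (Table 12 footnotes). Protocol 6.2.1.4 lists events that end treatment and can occur sooner. The end-of-treatment list (7.2.3) names no marrow. The end-of-study list (7.2.4) does, but the same section provides for visits that cannot be held. So the group is small but not excluded.

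**2. Does the formula settle the status?** For such a subject:

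- failure date = first dose, so time = 0 + 1 = 1 day, event;
- censoring date = first dose, so time = 0 + 1 = 1 day, censored.

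The two dates are equal, so taking the earlier one does not choose between event and censored.

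**3. The plan's own efficacy figure.** SAP 3.2 states an exact 80% interval of 5.5% to 45.0%, half-width 19.8%, for 10 subjects and 20% response. Clopper-Pearson for 2 of 10:

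- lower = 0.10 quantile of Beta(2, 9) = 5.45%
- upper = 0.90 quantile of Beta(3, 8) = 44.96%
- half-width = 19.75%

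The figure reproduces. The plan gives no precision figure for EFS.

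**4. Effect on the curve.** Inputs: n = 10 and 2 responders (SAP 3.2); c = number of living, unassessed subjects who left. The documents do not give c, so it is an assumption, shown from 0 to 4. The other 8 − c non-responders are assessed and fail on day 1. The Kaplan-Meier value just after day 1 is:

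- unassessed subjects as events: 1 − 8/10 = 0.20 for any c;
- censored on day 1 with the usual tie convention (events first): 1 − (8 − c)/10 = (2 + c)/10;
- removed from the risk set before the day-1 events: 1 − (8 − c)/(10 − c) = 2/(10 − c).

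| c | event | censored after day-1 events | removed before them |
|---|---|---|---|
| 0 | 0.20 | 0.20 | 0.20 |
| 1 | 0.20 | 0.30 | 0.22 |
| 2 | 0.20 | 0.40 | 0.25 |
| 3 | 0.20 | 0.50 | 0.29 |
| 4 | 0.20 | 0.60 | 0.33 |

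The Greenwood standard error at 0.20 is √(0.2 × 0.8/10) = 0.126. Under the usual tie convention, 1 or 2 such subjects shift the estimate by 0.10/0.126 = 0.8 or 0.20/0.126 = 1.6 standard errors. With these subjects as events, the curve after day 1 equals the 2/10 response rate, so the two endpoints agree.

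**The case against.** The strongest reply is that the SAP already answers the question: an unassessed subject is a non-responder, the failure sentence applies, and nothing is inflated. SAP section 10 favours that reading. It is a reasonable reading, but not a stated one, and at the primary analysis it would leave the day-1 censoring clause almost nothing to do. Equally, a reader might infer that the SAP definitely censors early drop-outs and so inflates the curve. The documents do not support that either. The inflation follows only if the censoring sentence is given precedence.

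The group is also narrower than all early drop-outs. After premature discontinuation the investigator is to make every effort to complete the end-of-treatment and end-of-study examinations (Protocol 6.2.1.4), and the latter include marrow. Subjects who stop drug are not automatically taken off study (8.1). Appendix E lets resistant disease be shown by blood, and hematology is scheduled at end of treatment. This all stands: it limits the group without emptying it. The documents do not show how often such departures would be for toxicity.

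Two further inferences go too far:

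- **Appendix E.** Its treatment-failure table contains the line "Patients who do not complete the first course of therapy", which seems to settle the matter. As extracted, the line sits in the row on death from indeterminate cause, after "Deaths occurring before completion of therapy, or <7 days following its completion". Its scope is unclear, and the EFS definition does not cite it.
- **Contradiction with the response rate.** Keeping unassessed subjects in the denominator implies that they count as non-responders, but no sentence says so. A proven contradiction between two secondary endpoints is therefore not available.

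Partial remission is a separate question. Importing Appendix E's phase I wording, "failure to achieve CR, CRi, or PR (phase I trials", would make a partial remission a non-response for the rate but not a failure for EFS, and that wording omits CRh* and morphologic leukemia-free state, both of which the SAP counts as responses.

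Finally, the curve is optional and the analysis exploratory. That lowers the stakes, though EFS stands in for a named secondary endpoint and is to be listed for every subject.

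**Conclusion.** The point holds as an unresolved conflict between two adjacent sentences of SAP section 5. It affects only living, treated subjects who leave with no evaluable post-baseline response assessment. If the censoring sentence is applied to them, the bias is upward under either handling of ties.

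The size rests on three things: the planning case of 2 responders in 10, an assumed count of 1 or 2 such subjects, and the tie convention. On those terms the estimate after day 1 moves from 0.20 to 0.30 or 0.40, or to 0.22 or 0.25 if the subjects are removed first. If there are none, or if they are scored as failures, there is no effect. It is worth correcting before analysis because coding the listing and any curve requires a choice that the text does not make.

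**What to change.** Amend the EFS definition in SAP section 5 along these lines:

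> A treated subject who leaves the study, or starts other AML therapy, without an evaluable post-baseline response assessment is a non-responder and a treatment failure; the event is dated at the first dose. A subject still on study and awaiting a first assessment at the data cut-off is censored at the first dose.

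Retain censoring at the last evaluable assessment for subjects without an event. The day-1 censoring date should not simply be deleted: it is the only one available for subjects pending at a cut-off, for example at the efficacy interim analysis after dose escalation (SAP 7.1).

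In SAP 9.5.2, state the matching rule for the response rate: treated subjects who leave without an evaluable assessment stay in the denominator and count as non-responders.

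The cost is a few sentences and a possibly slightly less favourable exploratory curve. No new data or visits are needed.

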## **6. Analysis Sets**

### **6.1 Safety Analysis Set**

All subjects that are enrolled and received at least 1 dose of AMG 673

### **6.2 Pharmacokinetic/Pharmacodynamic Analyses Set(s)**

The PK Analysis Set will contain all subjects who have received at least 1 dose of the investigational product and have at least 1 PK sample collected. These subjects will be evaluated for PK analysis unless the number of data points required for analysis is not enough, or significant protocol deviations have affected the data, or if key dosing or sampling information is missing.

## **7. Planned Analyses**

The following data analyses are planned:

(1) Primary analysis after all dose escalation and dose-expansion subjects had the opportunity to receive up to 2 cycles of treatment.

(2) Final analysis after all subjects have ended the study

### **7.1 Interim Analysis and Early Stopping Guidelines**

Safety data will be reviewed on an ongoing basis. Based on accumulating toxicity information, BLRM will be used to make dosing recommendations. In DLRMs, Amgen, in consultation with the site investigators, will review the BLRM recommended dose level and will review all available cumulative data by cohort prior to making dose escalation decisions. As a sensitivity analysis, a one-parameter Continual Reassessment Method (CRM) model may be used to estimate the dose-toxicity relationship to help making dose escalation decisions. Adverse events and DLTs observed in all subjects will be evaluated continually and fully integrated into all DLRMs and considered in all enrolment and dosing decisions.

An interim analysis for efficacy parameters will be conducted after dose escalation is completed.

### Dose Level Review Team (DLRT)

DLRMs will be held to review data, monitor safety, and make decisions on dose escalation / change, or changes in pre-medication. The DLRT will be composed of the investigators or designees, and the following Amgen representatives: early development leader/**Medical Monitor and** global safety officer, or their approved designees, clinical study manager, **and** biostatistician **and** PK scientist (optional). Other functional area representatives **may participate** as appropriate. The following members, **or their qualified designees**, are responsible for DLRT recommendations: investigators, Amgen medical monitor, and global safety officer.

All available study data, including data collected after the initial DLT window, and including demographics, IP administration, medical history, concomitant medications, adverse events, ECGs, vital signs, laboratory data, and PK/PD information will be reviewed. In addition to DLTs, all  $\geq$  grade 3 toxicities not meeting DLT criteria will be reviewed and may be considered in DLRT decisions. Modeling of available potential safety risk data (eg, for thrombocytopenia) to predict safety risk for dose escalation decisions may also be considered.

A quorum as defined below must be in attendance for the DLRM. The quorum is defined as  $> 50\%$  of the responsible members or their qualified designee (ie, sub-investigator or research nurse or study coordinator), as well as **the** Amgen representatives **responsible for DLRT recommendations** listed above. **Investigators that are not able to participate in the meeting (eg, due to time difference) may also provide their vote in writing (eg, by email to Sponsor) after review of the data discussed at the meeting.** The early development leader or designee must attend for the quorum to be reached.

The DLRM will be rescheduled if a quorum is not reached.

The following decisions will be made by the DLRT:

- dose escalation / de-escalation decisions
- administration of additional infusions on D12/D19 of a cycle
- number of subjects per cohort
- continuation, delay or termination of dosing
- implementation of dose step(s)
- change of the D1/D5/D12/D19 dosing scheme within the pre-specified window of +/- 1 day

- extension of the treatment-free interval between treatment cycles

Subjects' cytogenetic profiles (eg, potentially higher cytokine release in monocytic AML) should be taken into consideration for DLRT decisions.

In the expansion phase, all available study data will be reviewed (with recruitment ongoing) by the DLRT once the first 5 subjects have at least completed their first treatment cycle plus two weeks or dropped out of treatment / study, whichever occurs earlier. Ad hoc meetings may be convened any time in case of important safety event

## **7.2 Primary Analysis**

The primary analysis will occur when target enrollment is complete, and each subject had the opportunity to receive up to 2 cycles of treatment or terminated the study early

## **7.3 Final Analysis**

A final analysis is planned after all dose-escalation cohorts and dose-expansion subjects have ended the study. Primary and final analysis may be combined in case all subjects have ended study close to the time point of the primary analysis.

## **8. Data Screening and Acceptance**

### **8.1 General Principles**

The objective of the data screening is to assess the quantity, quality, and statistical characteristics of the data relative to the requirements of the planned analyses.

### **8.2 Data Handling and Electronic Transfer of Data**

The Amgen Global Study Operations-Data Management (GSO-DM) department will provide all data to be used in the planned analyses. This study will use the RAVE a base.

### **8.3 Handling of Missing and Incomplete Data**

The following imputation for missing or incomplete data will be performed if required: Incomplete adverse event and concomitant medication dates missing data will be imputed as described in [Appendix A](#).

Non-pharmacokinetic measurements (eg, biomarker data) that are below the lower limit of quantification will be considered equal to half of the lower limit of quantification for all analyses unless specified otherwise.

The following imputation of missing values will be done:

- Incomplete adverse event and concomitant medication dates will be imputed as per [Appendix A](#). If imputed dates are used, then they will be identified as such in the final study report.
- Laboratory measurements that are below the quantification limits will be considered equal to the lower limit of quantification for all analyses unless explicitly noted otherwise.
- Biomarker data that are below the quantification limits will be considered equal to half of the lower limit of quantification for all analyses unless specified otherwise.

PK concentrations that are below the quantification limits will be set to zero when engaging non-compartmental model to compute PK parameters.

#### **8.4 Detection of Bias**

Lack of protocol compliance and the potential for biased statistical analyses will be examined by assessing the incidence of important protocol deviations in each cohort. The clinical study team will identify and document the criteria for important protocol deviations.

#### **8.5 Outliers**

Pharmacokinetic (PK) concentration data will be evaluated for outliers by visual inspection, and decisions to re-assay individual samples will be made in accordance with standard pharmacokinetic evaluation practice.

#### **8.6 Distributional Characteristics**

Where appropriate, the assumptions underlying the proposed statistical methodologies will be assessed. If required data transformations or alternative non-parametric methods of analyses will be utilized.

#### **8.7 Validation of Statistical Analyses**

Programs will be developed and maintained and output will be verified in accordance with current risk-based quality control procedures.

Tables, figures, and listings will be produced with validated standard macro programs where standard macros can produce the specified outputs.

The production environment for statistical analyses consists of Amgen-supported versions of statistical analysis software; for example, the SAS System version [9.4](#) or later.

## 9. Statistical Methods of Analysis

### 9.1 General Considerations

[figure not shown]
Descriptive statistics will be provided for selected demographics, safety, PK, PD and biomarker data by dose, dose schedule, and time as appropriate. Descriptive statistics on continuous data will include means, medians, standard deviations and ranges, while categorical data will be summarized using frequency counts and percentages. Graphical summaries of the data may also be presented. A two-parameter BLRM will be used to estimate the dose-toxicity relationship.

[figure not shown]
A two-parameter Bayesian Logistic Regression Model (BLRM) is used to guide dose exploration. The maximum tolerated dose (MTD) target Toxicity Probability Interval (TPI) for dose-limiting toxicity (DLT) is (0.20, 0.33] and TPIs of (0.33, 0.60] and (0.60, 1.00] are defined as excessive and unacceptable, respectively. The design seeks to identify a dose most likely to have a DLT rate in the target TPI, but with over-dose control that limits the possibility the dose has an excessive or unacceptable DLT rate ([Babb et al 1998](#)). The probability of a DLT at dose level  $d_i$  is assumed to follow a Bernoulli distribution with probability  $p_i$  where the logit of  $p_i$  increases linearly with the log of the standardized dose in the following 2-parameter logistic model:

$$\log [p_i / (1-p_i)] = \text{logit}(p_i) = \log[a] + \exp(\log[b]) \log (d_i / d_{ref})$$

where  $a$  and  $b$  are random variables and  $d_{ref}$  is one of the planned dose selected as the reference dose.

A bi-variate normal prior distribution ([Neuenschwander et al 2008](#)) was selected for  $\theta = (\log a, \log b)$  where the probability that the true DLT rate is  $\leq 0.40$  at the lowest planned dose is 0.90 and the probability the true DLT rate is  $\leq 0.05$  at the reference dose is 0.05. **The prior distribution of BLRM for step dosing may be adjusted based on the accumulative data. For example, the starting dose and the reference dose of BLRM prior to estimate MTD2 may be based on MTD1 and the expected MTD for MTD2.** The operating characteristics of the 2-parameter BLRM design were evaluated via simulation for **schedule A and B separately.**

